3.2 Exclusion Criteria

Patients who meet any of the following criteria will be excluded from the study.

1. TMZ-Radiotherapy administration or radiotherapy within 12 weeks of the first documented progression. Other chemotherapy including Temozolomide monotherapy, immunotherapy or investigational agents must be stopped a minimum of 4 weeks prior to the first dose of BBI608.
2. Previous treatment with bevacizumab or other anti-VEGF agents
3. Any prior anti-cancer treatment for disease recurrence/progression.
4. More than one instance of disease recurrence/progression.
5. Presence of diffuse leptomeningeal disease, gliomatosis cerebri, or infratentorial disease.
6. Major surgery within 4 weeks prior to enrollment.

- a. Patients who had repeat surgical resection to treat GBM are allowed to start the Arm B portion of this study after 15 days of the surgery.
7. Pregnant or breastfeeding.
8. Treatment with EIAEDs within 14 days of first dose of BBI608.
9. Significant gastrointestinal disorder(s) that would, in the opinion of the Principal Investigator, prevent absorption of an orally available agent (e.g., Crohn's disease, ulcerative colitis, extensive gastric resection and small intestinal resection).
10. Unable or unwilling to swallow BBI608 capsules daily.
11. Prior treatment with BBI608.
12. Uncontrolled intercurrent illness including, but not limited to ongoing or active infection, clinically significant non-healing or healing wounds, symptomatic congestive heart failure within the past 12 months, unstable angina pectoris, cardiac arrhythmia, significant pulmonary disease (shortness of breath at rest or mild exertion), uncontrolled infection, HIV, chronic hepatitis B, chronic hepatitis C, immunosuppressive disease, concurrent neurodegenerative disease, chronic renal disease/failure, or psychiatric illness/social situations that would limit compliance with study requirements.
13. Known hypersensitivity to TMZ.
14. History of intolerance to TMZ with need to discontinue TMZ or decrease dose to < 150 mg/m² for days 1 through 5 of each 28 day cycle.

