4 INVESTIGATIONAL PLAN

4.1 Overall Study Design

This is an open-label, multi-center Phase Ib/II, study of BBI608 administered in combination with TMZ to patients with recurrent or progressive GBM who have not received prior bevacizumab therapy. The study is designed to explore the safety, tolerability and pharmacokinetics of BBI608, and the preliminary anti-cancer activity of BBI608 in combination with TMZ, in adults with recurrent or progressive GBM who have not received prior treatment with bevacizumab and who may or may not be eligible for further surgical resection. The primary efficacy endpoint will be PFS-6. Secondary efficacy endpoints will include median PFS, OS, DCR and ORR.

Arm A will include patients who are candidates for repeat surgical resection. These patients will receive 7 (\pm 2) days of BBI608 monotherapy at a dose level of 480 mg twice daily (960 mg total daily dose – Initial Dose) prior to resection. Following surgical clinical recovery, and on a date between 15-28 days following the date of surgery, BBI608 (480 mg twice daily) will be restarted in combination with TMZ (150 mg/m² on days 1 through 5 of each 28-day cycle). If a patient does not recover from surgical resection sufficiently within 28 days to resume oral therapy with BBI608 plus TMZ, the patient should be withdrawn from study. Combination therapy will continue until disease progression or another discontinuation criterion is met. The dose of TMZ can be increased to 200 mg/m² for those patients who complete at least one cycle at 150 mg/m² in combination with BBI608.

Arm B will include patients who are either not candidates for repeat surgical resection or have undergone repeat surgical resection prior to enter the study. These patients will receive BBI608 (480 mg twice daily) in combination with TMZ (150 mg/m² administered for days 1 through 5 of each 28 day cycle) and continue treatment until disease progression or another discontinuation criterion is met. The dose of TMZ can be increased to 200 mg/m² for those patients who complete at least one cycle at 150 mg/m² in combination with BBI608.

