5.3 Pre-Study Evaluations (Baseline)

After written informed consent is obtained according to ICH-GCP and local regulations, the patient will be evaluated for inclusion and exclusion criteria according to the eligibility criteria listed in Section 3.

The following will be evaluated and documented within 10 days prior to first dose of BBI608:

- Medical history
- Physical examination including a neurologic exam
- ECOG performance status score (see APPENDIX C)
- Vital signs (weight, temperature, blood pressure, height, respiration and pulse)
- Adverse Event assessment (from the date of informed consent)
- Assessment of concomitant medications from 28 days prior to the start of study treatment
- Hematology (see Section 6.3)
- Biochemistry (see Section 6.3)
- Urinalysis (see Section 6.3)
- Serum pregnancy test (if applicable)
- Archival tissue will be obtained as described in the Laboratory Manual once the patient has been enrolled.
- 12-lead electrocardiogram (ECG)
- Tumor measurement [magnetic resonance imaging (MRI) scan]*

* MRI scan performed within 28 days of the first scheduled dose of BBI608 can be used for baseline assessment if it was performed while off steroids or on a stable or decreasing steroid dosage for at least 5 days; otherwise, MRI should be performed within 14 days of dosing. This will be the baseline scan for patients in ARM B; repeat MRI obtained within 48-72 hours following surgery will be the baseline scan for the patients in ARM A for purposes of response assessment.

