9.3 Response Criteria

Radiographic response should be determined in comparison to the tumor measurement obtained at pretreatment baseline for determination of response, and the smallest tumor measurement at either pretreatment baseline or after initiation of therapy for determination of progression. For patients in Arm A who undergo surgical resection, the post-operative baseline scan (performed 48-72 hours after surgery) should be used for response assessment.

Response criteria are outlined below. In the event that the radiographic changes are equivocal and it is unclear whether the patient is stable or has developed progressive disease, it is permissible to continue treatment and observe the patient closely, for example at 4-week intervals. If subsequent imaging studies demonstrate that progression has occurred, the date of progression should be the date of the scan at which progression was first suspected.

Complete Response*

Requires ALL of the following:

1. Complete disappearance of all enhancing measurable and non-measurable disease sustained for at least 4 weeks.
2. No new lesions.
3. Stable or improved non-enhancing (T2/FLAIR) lesions.
4. Patients must be off corticosteroids (or on physiologic replacement doses only).
5. Patients must be stable or improved clinically.[#]

Partial Response*

Requires ALL of the following:

1. Greater than or equal to 50% decrease compared to baseline in the sum of products of perpendicular diameters of all measurable enhancing lesions sustained for at least 4 weeks.
2. No progression of non-measurable disease.
3. No new lesions.
4. Stable or improved non-enhancing (T2/FLAIR) lesions on same or lower dose of corticosteroids compared to baseline scan.
5. The corticosteroid dose at the time of the scan evaluation should be no greater than the dose at time of baseline scan.
6. Patients must be stable or improved clinically.#

Stable Disease

Requires ALL of the following:

1. Does not qualify for complete response, partial response, or progression.

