7.2. Definition of Baseline Values

The baseline value is defined as the value collected at the time closest to, but prior to the start of study drug administration (BBI608 or TMZ, whichever was administered first). Values will be considered baseline if they are up to 10 days prior to first dose. An MRI scan performed within 28 days of the first schedule dose of BBI608 can be used for baseline assessment if it was performed while the patient was off steroids or on a stable or decreasing steroid dosage for at least 5 days; otherwise, MRI should be performed within 14 days of dosing. This will be the baseline scan for patients in Arm B; repeat MRI obtained within 48-72 hours following surgery will be the baseline scan for the patients in Arm A for purposes of response assessment.

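### Arm B patients resected before entry can have a pre-operative MRI as baseline, which can inflate disease control (and sometimes response) and delay first progression by about one scan interval

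*Protocol*

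**What the plan says.** **Who enters.** Protocol 4.1 places in Arm B, besides patients who cannot be resected, those who "have undergone repeat surgical resection prior to enter the study". Exclusion 6a in section 3.2 says that they "are allowed to start the Arm B portion of this study after 15 days of the surgery".

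**Which scan is baseline.** Protocol 5.3 says that an "MRI scan performed within 28 days of the first scheduled dose of BBI608 can be used for baseline assessment", provided the patient was off steroids or had been on a stable or falling dose for at least 5 days; "otherwise, MRI should be performed within 14 days of dosing". It continues: "This will be the baseline scan for patients in ARM B". Appendix B, note 6, repeats the 28-day window without the steroid condition. SAP 7.2 opens with a general rule that takes the value nearest to, and before, first dose. It then repeats the MRI rule of 5.3, including "This will be the baseline scan for patients in Arm B".

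**Post-operative baseline.** Protocol 5.3 says that a "repeat MRI obtained within 48-72 hours following surgery will be the baseline scan for the patients in ARM A". Section 9.3 carries the same limit: "For patients in Arm A who undergo surgical resection, the post-operative baseline scan" is the one to use. Section 5.5, Appendix A note 8 and SAP 7.2 also confine the rule to Arm A, and section 5.4.2 applies to Arm A alone.

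No section requires the Arm B baseline MRI to post-date a resection done before entry.

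**The concern.** The plan recognises for Arm A that a scan taken before surgery is the wrong reference after surgery. It does not carry that principle to Arm B patients who reach the same state by having their operation before enrolment.

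Two rules in Protocol 9.3 depend on the reference scan:

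- **Response** is a reduction from baseline. If baseline is pre-operative, the surgeon's reduction is counted as if treatment had produced it.
- **Progression** is judged against the smallest measurement at baseline or after therapy starts. A post-operative scan taken before dosing and not designated as baseline is neither, so the true low point can drop out of the comparison.

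Measurability is affected too. Protocol section 9 treats tumour around a surgical cavity as non-measurable unless it has a nodule of at least 10 mm, and 9.3 bars patients with only non-measurable disease from CR or PR. A pre-operative baseline can make such a patient look measurable and so eligible for a response.

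DCR, ORR and the PFS curve are at stake for the exposed Arm B patients, and PFS-6 to a lesser degree.

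**Working it through.** **1. The plan's own figure.** Protocol 10.2 and SAP 4.2.2 state that with n = 30 and PFS-6 of 20% (6/30), the exact two-sided 80% lower bound exceeds 10%. The Clopper-Pearson lower limit is the 0.10 quantile of Beta(6, 25) = 10.9%, and the upper limit is 32.5%. The stated figure is reproduced. It serves below only as a scale.

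**2. Which scans qualify.** If dosing starts S days after surgery, a scan up to 28 - S days before surgery lies within the 28-day window.

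| S (days) | Scan may precede surgery by up to |
|---|---|
| 15 | 13 days |
| 20 | 8 days |
| 27 | 1 day |
| 28 or more | none |

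Under the 14-day fallback, 14 - 15 = -1, so that scan is always post-operative.

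**3. Size thresholds.** Let r be the residual after surgery as a fraction of the pre-operative sum of products (assumed; not in the documents). Against a pre-operative baseline, the PR size criterion is still met up to 0.5/r times the post-operative size, and size-based PD is avoided up to 1.25/r times. Against a post-operative baseline, PD starts above 1.25 times.

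| r | PR size met up to | No size PD up to |
|---|---|---|
| 0.05 | 10x | 25x |
| 0.10 | 5x | 12.5x |
| 0.20 | 2.5x | 6.25x |
| 0.40 | 1.25x | 3.1x |

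**4. Fast regrowth (illustration).** Take 10 cm² before surgery, 1 cm² after and 4 cm² at week 8.

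- Against the post-operative scan: (4 - 1)/1 = +300%, PD.
- Against the pre-operative scan: (4 - 10)/10 = -60%, within the PR size range.

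Now follow the patient, assuming constant exponential growth from surgery on day -15 to week 8 (15 + 56 = 71 days). The rate is ln(4)/71 = 0.0195 per day.

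- Four weeks later: 4 × exp(0.0195 × 28) ≈ 6.9 cm². That is -31% from 10 and +73% from the low point of 4. PR is not confirmed, and this is PD if scanned.
- Week 16: 4 × exp(0.0195 × 56) ≈ 12 cm², about three times the low point, so PD.

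Under the SAP Appendix 1.1 derivation, a PR followed by PD scores as SD. The patient counts in DCR, not in ORR. First PD moves from week 8 to week 16 at the latest on the scheduled scans.

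**5. Slow regrowth (illustration).** Take 10 cm² before surgery, 1 cm² after, and 1 cm² both at week 8 and four weeks later. Against the post-operative scan the change is 0% (SD). Against the pre-operative scan it is (1 - 10)/10 = -90% twice, four weeks apart. The size part of a confirmed PR is then met by surgery alone. This adds 1/30 = 3.3 points to ORR if the other PR criteria hold.

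**6. PFS-6.** Six months in the SAP is 6 × 30.4375 = 182.6 days, so the scans at weeks 8, 16 and 24 (day 168) all precede it. For the step 4 patient to become a PFS-6 success, the tumour must stay at or below 4 × 1.25 = 5 cm² at weeks 16 and 24 after quadrupling by week 8. If one of six successes did arise that way, the true count would be 5/30, with an exact 80% lower bound of 8.3% against 10.9% for 6/30. The Kaplan-Meier log(-log) limits without censoring are 9.1% and 11.6%.

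**The case against.** The strongest case on the other side is that the plan has several partial safeguards, and most of it stands.

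- **Steroid condition.** The 28-day scan qualifies under 5.3 and SAP 7.2 only if the steroid condition is met. Otherwise the 14-day rule forces a post-operative scan. This stands, although Appendix B omits the condition.
- **Nearest-to-dose rule.** If a post-operative pre-dose MRI exists, SAP 7.2's general rule points to it. This stands, but no such scan is required, and the MRI-specific sentence still accepts any qualifying scan in the window.
- **Confirmation.** PR must be sustained for at least 4 weeks and be confirmed, with T2/FLAIR, steroid and clinical conditions also met. A reader might infer from the -60% reading that fast regrowth yields a false responder. Step 4 shows that at constant growth it does not.
- **Running low point.** Later progression is judged against the smallest on-study measurement. A reader might infer that PFS-6 in Arm B is biased upward by 3.3 points for each such patient. The documents do not support that: the error usually ends by week 16, before 6 months.
- **Other PD criteria.** A new lesion, T2/FLAIR increase or clinical decline can still trigger PD. This stands in part. SAP Appendix 1.2 does not count symptomatic deterioration without radiographic confirmation, and regrowth at the operated site may not count as new if the baseline scan shows tumour there.
- **Arm membership.** The synopsis and SAP 2.1 describe Arm B only as patients who are not candidates for resection, and exclusion 3, read literally, conflicts with 6a. Those passages need reconciling, but 4.1 and 6a expressly admit the group.

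**Conclusion.** The gap is real and narrow. It concerns Arm B patients resected before entry who start less than 28 days after surgery, whose pre-operative scan met the steroid condition, and who have no later pre-dose scan. Their number is not given and could be zero, so the supported wording is that results can be inflated, not that they are.

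For each such patient:

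- **DCR** can be inflated directly.
- **ORR** can be inflated where regrowth is slow or the resection near-complete, so that the reduction is sustained and confirmed.
- **First PD** can be delayed by about one 8-week interval, which affects the PFS curve and possibly its median.
- **PFS-6** changes only if rapid early regrowth is followed by near-arrest to 6 months. That is uncommon, but with n = 30 one such patient would move the 80% lower bound across 10%.

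The sizes rest on assumed residual fractions and, for the time course, on constant exponential growth. The 3.3 points per patient is a ceiling that assumes 30 patients and, for PFS-6, no censoring. The change is worth making because the rule can give a wrong call and is cheap to correct.

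**What to change.** **Protocol 5.3, 9.3 and Appendix B, and SAP 7.2.** State that for Arm B patients with a repeat resection before entry, only an MRI taken after that surgery and before first dose may be the baseline for response and progression, as already done for Arm A. Carry the steroid condition into Appendix B so that it agrees with 5.3.

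**SAP, for data already collected.** SAP 8.1.1 says that follow-up was ended after 29JUN2018, so a missing pre-dose scan cannot now be obtained. The rule must work on existing scans:

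1. Select the post-operative pre-dose scan wherever one exists.
2. List every patient who has only a pre-operative scan.
3. Do not count those patients as responders or as disease control. SAP 7.1 already treats a missing baseline tumour evaluation this way.
4. Report PFS-6 with and without them. State how they enter the first version, because row 1 of SAP Table 4 would otherwise censor them at first dose for lack of a baseline.

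**Cost.** One sentence in each place and one listing. A few patients may lose evaluability for response, and ORR and DCR may be slightly lower. Treatment and sample size do not change.

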3.3 Number of Patients

The exact number of patients estimated for this trial is dependent on the number of patient cohorts investigated based on the toxicity encountered. It is expected that approximately 30 patients (including those enrolled to the DLT evaluation cohorts) will be enrolled in each arm of this study.

4 INVESTIGATIONAL PLAN

4.1 Overall Study Design

This is an open-label, multi-center Phase Ib/II, study of BBI608 administered in combination with TMZ to patients with recurrent or progressive GBM who have not received prior bevacizumab therapy. The study is designed to explore the safety, tolerability and pharmacokinetics of BBI608, and the preliminary anti-cancer activity of BBI608 in combination with TMZ, in adults with recurrent or progressive GBM who have not received prior treatment with bevacizumab and who may or may not be eligible for further surgical resection. The primary efficacy endpoint will be PFS-6. Secondary efficacy endpoints will include median PFS, OS, DCR and ORR.

Arm A will include patients who are candidates for repeat surgical resection. These patients will receive 7 (\pm 2) days of BBI608 monotherapy at a dose level of 480 mg twice daily (960 mg total daily dose – Initial Dose) prior to resection. Following surgical clinical recovery, and on a date between 15-28 days following the date of surgery, BBI608 (480 mg twice daily) will be restarted in combination with TMZ (150 mg/m² on days 1 through 5 of each 28-day cycle). If a patient does not recover from surgical resection sufficiently within 28 days to resume oral therapy with BBI608 plus TMZ, the patient should be withdrawn from study. Combination therapy will continue until disease progression or another discontinuation criterion is met. The dose of TMZ can be increased to 200 mg/m² for those patients who complete at least one cycle at 150 mg/m² in combination with BBI608.

Arm B will include patients who are either not candidates for repeat surgical resection or have undergone repeat surgical resection prior to enter the study. These patients will receive BBI608 (480 mg twice daily) in combination with TMZ (150 mg/m² administered for days 1 through 5 of each 28 day cycle) and continue treatment until disease progression or another discontinuation criterion is met. The dose of TMZ can be increased to 200 mg/m² for those patients who complete at least one cycle at 150 mg/m² in combination with BBI608.

Initially, 6 patients will be enrolled into a safety cohort for each study arm. The 6-patient safety cohort will be evaluated for the occurrence of DLTs during the first 28 days of combination treatment. For patient in Arm A during the run-in period with BBI608 monotherapy, the same DLT rules as for the combination therapy will apply. Enrollment will be held if ≥ 2 patients are unable to undergo resection due to DLTs. Enrollment will also be held if ≥ 2 patients have an unexpected surgical complication.

For a given arm, if ≥ 2 out of 6 patients experience a DLT, then the BBI608 dose will be reduced for all patients in that arm to the next lower dose level of 240mg twice daily. Furthermore, an additional 6-patient safety cohort in that study arm will be enrolled at the reduced dose-level and evaluated for DLT as described below.

Recommended Phase 2 Dose (RP2D) will be defined as the dose-level evaluated at which ≤ 1 of 6 patients per cohort experiences a DLT.

An additional 24 patients may be enrolled at RP2D in each arm.

For both study arms, cycle length will be 28 days. Combination-therapy cycles will consist of BBI608 administration daily for 28 days and TMZ administration on days 1-5 of each cycle.

Tumor assessments using RANO criteria will be performed every eight weeks from the initiation of combination therapy with BBI608 and TMZ, or otherwise as clinically indicated.

Number of Subjects with DLT at a Given Dose Level for a Given Study Arm	Dose De-escalation Decision Rule
≤ 1 out of 6	This dose level will be considered RP2D for the combination regimen (BBI608+TMZ)
≥ 2 out of 6	Initial dose level will be reduced to a dose chosen by the Investigator and BBI medical monitor. Six (6) additional subjects will be entered at this lower dose level and evaluated for DLT over the first 28 days of combination therapy.

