In the phase Ib/DLT cohort portion of this study, for both Arms A and B, pharmacokinetics will be evaluated on Day 1 and Day 5 of combination therapy with BBI608 and TMZ. Pharmacodynamics will be evaluated in all patients who undergo surgical resection.

For patients in Arm A during the run- in period with BBI608 monotherapy, the same DLT rules as for the combination therapy will apply. Enrollment will be held if ≥ 2 patients are unable to undergo resection due to DLTs. Enrollment will also be held if ≥ 2 patients have an unexpected surgical complication.

Initial enrollment will be to a 6-patient safety cohort in each arm. These patients will be evaluated for the occurrence of DLT during the first 28 days of combination treatment with BBI608 and TMZ. If DLT is observed in ≥ 2 of 6 patients evaluable for DLT, the initial dose of BBI608 for all patients in that arm will be reduced to the next lower dose level of 240mg twice daily and an additional 6-patient safety cohort will be enrolled at that dose-level and evaluated for DLT as above. Enrollment will continue at a dose-level at which ≤ 1 of 6 patients experiences DLT. Dose modification is allowed according to the standard schedule for BBI608.

It is expected that up to 30 patients (including those enrolled to the DLT evaluation cohorts) will be enrolled in each arm.

For all patients on study, tumor assessments will be performed at eight-week intervals or as clinically indicated. Disease status will be assessed by contrast-enhanced magnetic resonance imaging (MRI) of the brain.

Progression Free Survival will be assessed from the date of enrollment until objective disease progression or death. Tumor response and progression will be evaluated using RANO criteria. Patients who are enrolled in Arm A but who do not undergo surgical resection will be considered evaluable for tumor response utilizing the same assessment criteria as employed for patients in Arm B. All patients will be followed for disease progression and included in time-to-event analyses.

Patients will continue treatment with BBI608 and TMZ until the investigator has determined that they are no longer clinically benefiting due to progression of

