5.4.2 Surgical Resection of Recurrent GBM

ONLY patients enrolled into Arm A will undergo surgical resection of GBM.

BBI608 will be administered for 7 (\pm 2) days prior to a planned surgical resection of recurrent GBM. BBI608 will be administered on the morning of the surgical procedure (Run-in Week 2 Day 8) and BBI608 will remain held pending clinical post-operative recovery of the patient as determined by the investigator, for up to 28 days after surgery. Tumor sample will be obtained at time of surgical resection from T1/gadolinium enhanced lesion(s) as well as T2/FLAIR infiltrating tumor lesions and will be used to investigate BBI608 presence in the resected tumor tissue and will be used for pharmacodynamics analysis (please see the Laboratory Manual for additional information). Additionally, blood sample will be obtained at time of surgery to evaluate BBI608 pharmacokinetic (PK) exposure in the plasma (please see the Laboratory Manual for additional information). The time of BBI608 administration on the day of surgery and the collection times of blood sample will be recorded.

Tumor samples that are obtained at the time of surgical resection and are labeled with study protocol identification number and patient identification number will be sent to a regulatory authority-approved tumor bank affiliated with the study site, or to the study site pathology department if the site does not have a regulatory authority-approved tumor bank. In the event

that there is difficulty with establishment of histological diagnosis, tumor tissue will be made available to the pathology department at all study sites. Processing of all tumor tissue will include creation of both fresh frozen samples for PK analysis as well as blocks of formalin fixed paraffin-embedded (FFPE) samples for PD analysis.

An MRI will be performed 48-72 hours following surgery and will be used as the baseline scan for the purposes of tumor response evaluation in the patients who undergo surgical resection.

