3.1.2. Phase II

Progression free survival (PFS) at 6 months of BBI608 administered in combination with TMZ: is defined as the proportion of patients who have survived without objective disease progression per RANO criteria for at least 6 months after enrollment.

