10.2. Appendix 1.2 Censoring for Time to Event Data

Table 4 summarizes the censoring rules for the PFS analysis and displays censoring hierarchy for this study. Table 5 shows the general reasons for PFS censoring and where the censoring hierarchy in **Table 4** came from.

Table 4 Event or Censor Time for PFS and Censoring Hierarchy

Censoring Hierarchy	Situation	Date of Event or Censor	Event / Censor
1	No baseline radiological tumor assessment available	Date of First Dose	Censored
2	New anticancer treatment started and no tumor progression	Date of previous adequate radiological assessment immediately prior to start of new therapy or Date of first dose, whichever comes later	Censored
3	Tumor progression (per RANO) documented after 2 scan intervals following previous adequate radiological tumor assessment	Date of previous adequate radiological assessment or Date of first dose, whichever comes later	Censored
4, 5	No tumor progression (per RANO) and subject lost to follow-up or withdrawal of consent	Date of last adequate radiological Assessment or Date of first dose, whichever comes later	Censored
6	No post baseline radiological tumor assessment available and no death reported within 2 scan intervals following the date of the first dose of study drug (BBI608)	Date of First Dose	Censored
7	No post baseline radiological tumor assessment available but death reported within 2 scan intervals following the date of the first dose of study drug (BBI608)	Date of Death	Event

	No tumor progression (per RANO) and no death reported within 2 scan intervals following last adequate radiological tumor assessment	Date of last adequate radiological tumor assessment or Date of first dose, whichever comes later	Censored
	No tumor progression (per RANO) but death reported within 2 scan intervals following last adequate radiological tumor assessment	Date of death	Event
	Tumor progression (per RANO) documented within 2 scan intervals following previous adequate radiological tumor assessment	Earliest of the target, non-target and new tumor assessment dates	Event

Notes: (1) Symptomatic deteriorations (i.e. symptomatic progressions, which are not radiographically confirmed) will not be considered as progressions.

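### SAP Table 4 censors at first dose a patient with no post-baseline scan who is known to have died between about day 113 and month 6; Arm A patients who never start the combination are most exposed

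*Protocol*

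**What the plan says.** **Endpoint.** SAP 3.1.2 defines PFS-6 as "the proportion of patients who have survived without objective disease progression per RANO criteria for at least 6 months after enrollment". SAP 10.1 makes death from any cause a PFS event, and SAP 8.2.2.2 censors only patients who have neither progressed nor died. SAP 8.2.2.2 estimates PFS-6 by Kaplan-Meier, with time counted from first dose and a month of 30.4375 days.

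**Arm A exit.** Under Protocol 4.1, if a patient has not recovered enough "within 28 days to resume oral therapy with BBI608 plus TMZ, the patient should be withdrawn from study". The synopsis nevertheless states: "All patients will be followed for disease progression and included in time-to-event analyses". Protocol 5.6 continues PFS and OS follow-up from medical records after the End of Study visit.

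**Scans.** Protocol 4.1: "Tumor assessments using RANO criteria will be performed every eight weeks from the initiation of combination therapy with BBI608 and TMZ". SAP 7.2: "repeat MRI obtained within 48-72 hours following surgery will be the baseline scan for the patients in Arm A". The End of Study visit lists a tumor measurement where applicable (Protocol 5.6), and Appendix A marks a tumor assessment at that visit.

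**Censoring.** Line 6 of SAP Table 4 covers this case: "No post baseline radiological tumor assessment available and no death reported within 2 scan intervals", counted from first dose. The patient is censored at first dose. Line 7 is its counterpart: with no post-baseline scan but a death inside that window, the death is an event on its date.

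**The concern.** An Arm A patient is in the Full Analysis Set from the first run-in dose. One who never starts the combination has no 8-weekly scan to come. If no other scan is done after baseline, only the date of death decides between lines 6 and 7. A death after two scan intervals but before month 6 is a known failure on the primary efficacy endpoint, recorded through the planned follow-up, and line 6 treats it as carrying no information. Failure to recover from surgery plausibly marks a poor prognosis, so this censoring is unlikely to be independent of outcome.

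Line 6 is not specific to Arm A. An Arm B patient who stops before the first scan, at about week 8, can meet it too. Arm A is more exposed because its scan clock starts only after run-in, surgery and recovery.

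**Working it through.** **1. The plan's own figure.** SAP 4.2.2 and Protocol 10.2 say that with N = 30 and PFS-6 = 20%, the exact two-sided 80% lower limit exceeds 10%. For 6/30 the lower limit is the 0.10 quantile of Beta(6, 25), which is 10.9%. The upper limit is 32.5%. The statement reproduces.

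**2. Timeline from first dose.**
- Surgery: run-in of 7 ± 2 days, so day 5 to 9.
- 28-day recovery limit: 5 + 28 = 33 to 9 + 28 = 37.
- First 8-weekly scan in patients who do continue (combination starts 15 to 28 days after surgery): 5 + 15 + 56 = 76 to 9 + 28 + 56 = 93.
- End of Study visit for a patient whose last dose is on the day of surgery (30 days after last dose, Protocol 5.7.1): day 35 to 39.

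**3. The lost window.** Two scan intervals = 2 × 56 = 112 days. Month 6 = 6 × 30.4375 = 182.6 days. Without a post-baseline scan, deaths to day 112 are events (line 7). Deaths from about day 113 to day 182 are censored at first dose (line 6). The window is 182.6 − 112 = 70.6 days.

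**4. Effect of each dropped death.** Take 30 patients, 6 event-free past month 6, no other censoring, and k deaths in the window. Counted as events, Kaplan-Meier gives 6/30 = 20.0% (80% CI 11.6 to 30.0, on the log cumulative hazard scale). Censored at first dose, it gives 6/(30 − k):

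| k | PFS-6 under Table 4 |
|---|---|
| 1 | 6/29 = 20.7% |
| 2 | 6/28 = 21.4% |
| 3 | 6/27 = 22.2% |
| 5 | 6/25 = 24.0% |

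**5. How many such deaths to expect.** The documents give neither the number of exits nor their survival. Assume 3 to 5 exits of 30 and exponential survival from first dose, with medians of 8.5 months (the TMZ figure in Protocol 1.2), 6 and 4 months. The probability of death in the window is S(112) − S(182.6) = 0.128, 0.154 and 0.175.
- Low end: 3 × 0.128 = 0.38 deaths, 6/29.62 = 20.3%.
- High end: 5 × 0.175 = 0.88 deaths, 6/29.12 = 20.6%.

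The inflation is 0.3 to 0.6 points. If survival is instead counted from day 36 (all exits alive at withdrawal), with medians of 2 to 8.5 months, the window probability is 0.141 to 0.233. The top of the range becomes 5 × 0.233 = 1.17 deaths, 6/28.83 = 20.8%.

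**6. If an End of Study scan is done.** With a progression-free scan at day 35 to 39, Table 4 counts deaths for a further 112 days, to day 147 to 151. Later deaths are censored at that scan, not at first dose. The lost window shrinks to between 182.6 − 151 = 31.6 and 182.6 − 147 = 35.6 days.

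**7. Table 5 against Table 4.** Line 3 of Table 5 censors an event more than 2 weeks after the last adequate assessment or start date; Table 4 uses two scan intervals. Taken literally, 2 weeks would censor every death after withdrawal in an unscanned Arm A patient (day 33 or later). It would also censor almost any progression found on an 8-weekly scan, so it can hardly be intended. As written, though, the tables conflict.

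**The case against.** The case against giving this weight is substantial, and most of it stands.

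- **A reader might infer that every death before month 6 is lost.** Table 4 does not say that. Line 7 counts deaths to day 112. With survival counted from day 36 and medians of 2 to 8.5 months, 57% to 71% of deaths between withdrawal and month 6 are events.
- **A reader might infer that withdrawal under 4.1 triggers the censoring.** It does not. Lines 4 and 5 concern withdrawn consent and loss to follow-up. The synopsis and Protocol 5.6 keep these patients in follow-up. The trigger is the absent scan.
- **A scan may exist.** Appendix A marks one at End of Study, scans are allowed when clinically indicated, and later imaging is collected passively. Any adequate post-baseline scan takes the patient out of line 6.
- **A reader might take 22% to 24% as the likely result.** Those values require all 3 or 5 exits to be deaths inside the window. The expected number under the assumptions above is about 0.4 to 0.9.
- **A reader might say that line 6 always biases upward.** It also drops unscanned patients who are alive at month 6 (61% at a median of 8.5 months, since 2^(−6/8.5) = 0.613). Its net direction depends on the true PFS-6 in this group. Only the discarded deaths, taken alone, push upward.
- **The protocol's primary efficacy population is Per Protocol** (10.1, 10.3). It excludes patients who never receive TMZ. The SAP defines no such set and defines PFS in the Full Analysis Set, so the point concerns the SAP's analysis.

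What remains is that a stated rule discards known failures on the primary efficacy endpoint, contrary to the SAP's own definitions.

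**Conclusion.** The concern holds in a narrow form. In a patient without a post-baseline scan, a known death from about day 113 to month 6 is censored at first dose, although SAP 3.1.2, 8.2.2.2 and 10.1 make it a PFS-6 failure. Each such death adds about 0.7 points to a true 20%. The expected total is about 0.3 to 0.6 points for 3 to 5 exits, or up to 0.8 if survival is counted from withdrawal with a median as short as 2 months. This is small beside an exact 80% interval of 10.9% to 32.5%.

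The sizes rest on assumed numbers of exits, exponential survival, an 8-week scan interval and no End of Study scan. The contradiction between rule and definition rests on none of the survival assumptions. The documents do not support a claim of large or invariably upward bias, or of a defect confined to Arm A.

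**What to change.** 1. **SAP Table 4, for PFS-6.** Count any known death on or before month 6, in a patient without earlier documented progression, as an event at the date of death, whether or not a post-baseline scan exists and however long after the last scan. State how this ranks against line 2 (new anticancer therapy), which now comes first.
2. **Sensitivity analysis.** Report PFS-6 under the present rule as well, with the number of unscanned patients still censored at first dose, by arm.
3. **Reconcile Table 5 line 3 with Table 4** (2 weeks against two scan intervals).
4. **Reconcile the withdrawal wording in Protocol 4.1** with the follow-up stated in the synopsis and 5.6, so that it is clear whether these patients remain in PFS and OS follow-up.

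**Cost.** Items 1 to 3 are edits to the SAP tables plus one extra analysis. They use death dates already collected, which matters because SAP 8.1.1 says the sponsor ended all follow-up after 29 June 2018. Item 4 clarifies wording. PFS-6 becomes slightly less favourable. Because unscanned survivors are still censored at first dose while all known deaths count, the estimate may lean slightly conservative; the count in item 2 lets readers judge by how much.
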